 230 by trend, PSQI scores were reduced in the Blue Light group ($p =$
 231 .07), suggesting improvement. Of note, in contrast to the Amber
 232 Light group, for which sleep quality remained clinically abnormal
 233 (i.e., PSQI ≥ 5), the post-treatment PSQI mean reflected good sleep
 234 quality for the Blue Light group (i.e., PSQI < 5). These findings
 235 suggest that BL was more effective in improving subjective sleep
 236 quality than the PL treatment.

237 Actigraphic Sleep: Participants were monitored using wrist
 238 actigraphy for the duration of the study (1-week before treatment and throughout the treatment period).
 239 We compared actigraphic sleep between the baseline week and the final week of the study. After removal
 240 of one outlier ($z > 2.5$), participants in the BL group ($n = 6$) showed an increase in the minutes of sleep
 241 objectively measured by wrist actigraphy compared to the PL group ($n = 5$) (see Figure 4). On the whole,
 242 those in the amber placebo group improved by only 8.1 minutes of additional sleep per night, whereas
 243 those in the active BL group gained nearly twice as many minutes of sleep per night on average (i.e., 15.0
 244 minutes). Findings suggest that BL was associated with greater
 245 improvement in objective sleep quantity than PL.

246 Objective Sleepiness/Alertness. On an objective measure of
 247 sleepiness, participants were monitored with
 248 electroencephalography (EEG) while
 249 attempting to sleep for 20 minutes in a
 250 quiet, darkened room. Figure 5 shows
 251 daytime sleepiness, as measured with the
 252 Multiple Sleep Latency Test (MSLT) at
 253 11:50am, 1:50pm and 3:50pm pre- and
 254 post-intervention by group. There was a
 255 significant change in sleep onset latency
 256 between pre- and post-treatment by
 257 group ($p=.02$), with the BL group taking
 258 longer to fall asleep in sleep-conducive

FORM: Application for Human Research

| NUMBER | FORM DATE | PAGE |
|--------|-----------|----------|
| F200 | 02/2014 | 11 of 44 |

259 conditions than the PL group. This indicates greater enhancement of alertness in the BL group following
 260 treatment compared to the PL condition.

261 **Psychomotor Vigilance Test (PVT):** The PVT is a 10-minute computerized measure of sustained
 262 attention and psychomotor vigilance that has been shown to be exquisitely sensitive to sleep deprivation.

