**FORM: Application for Human Research**

| NUMBER | FORM DATE | PAGE |
|--------|-----------|----------|
| F200 | 02/2014 | 14 of 44 |

360 function, alterations in proton metabolites in the limbic system and medial prefrontal cortex, and reduced
361 PTSD symptom severity at follow-up assessment. The following are the Specific Aims and Hypotheses:

362 **AIM 1:** Evidence suggests that morning bright light therapy suppresses daytime melatonin and
363 leads to an entrainment of the circadian rhythm that modulates daytime alertness and nighttime sleep.
364 The first objective will be to assess the validity of this effect in PTSD patients.

365 **Hypothesis 1: Six weeks of BLT will improve sleep relative to PL among PTSD subjects.**

366 **1a:** Six weeks of morning blue light therapy (BLT) will improve objective and subjective
367 measures of sleep duration and quality as measured by actigraphy, sleep logs, sleep scales, and
368 polysomnography relative to an amber light placebo therapy (PL) condition.

369 **AIM 2:** If light therapy is successful in entraining the circadian rhythm and improving nighttime
370 sleep in patients with PTSD, this should be associated with improvement in symptoms and cognitive
371 functioning, as sleep has been shown to be critical in the process of extinguishing conditioned fears.
372 Therefore, the second Aim is to evaluate the association between changes in sleep patterns and
373 improvement in symptom expression, emotional wellbeing, and cognitive functioning in patients with
374 PTSD. However, even if Aim 1 is not successful, the present study will provide important cross-sectional
375 data regarding the relationship between measured sleep, cognitive functioning, and fear extinction in
376 individuals with PTSD.

377 **Hypothesis 2: BL will improve cognitive functioning, symptoms of PTSD, and generalization of**
378 **fear extinction relative to PL.**

379 **2a:** Six weeks of BL will improve measures of neurocognitive (i.e., memory and executive
380 functions) and mood functioning relative to PL.

381 **2b:** The PTSD group receiving six weeks of BL will show significant reduction in self-
382 reported symptom scores on the PTSD symptom checklist and CAPS, lower emotional distress on clinical
383 measures, and greater *generalization of conditioned fear extinction* relative to the PTSD group receiving
384 PL.

385 **AIM 3:** At present, there are no known studies that have examined the neurobiological correlates

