**FORM: Application for Human Research**

| NUMBER | FORM DATE | PAGE |
|--------|-----------|----------|
| F200 | 02/2014 | 15 of 44 |

402 **3d:** Relative to PL, six weeks of BL will be associated with increased levels of GABA and
403 reduced glutamate in the amygdala-hippocampal complex and anterior cingulate gyrus as measured by
404 proton magnetic resonance spectroscopy (1H MRS).

405 **3e:** Relative to PL, six weeks of BL will produce increased levels of N-acetyl-aspartate
406 (NAA), choline (Cho), and reduced phosphocreatine (Cr) within the amygdala-hippocampal complex and
407 anterior cingulate gyrus.

408 **AIM 4:** The fourth Aim is to demonstrate whether changes in subjective and objective measures
409 of sleep are associated with changes in symptom severity, cognitive functioning, brain activation, and
410 neurochemistry. Regardless of the success of the light therapy approach outcome in Aim 1, the available
411 data will provide some of the first longitudinal data examining changes in sleep patterns over time in
412 individuals with PTSD and their correlation with these other metrics. Thus, useful data will be acquired
413 even if the primary hypothesis of Aim 1 is not supported.

414 **Hypothesis 4: Improvements in sleep noted in Hypothesis 1, will be linearly correlated with
415 improvements in cognitive and symptom functioning in Hypothesis 2 and structural and functional
416 brain changes in Hypothesis 3.**

417 **4a:** Changes in sleep parameters identified in Hypothesis 1 will correlate with
418 improvements in memory, executive functioning, and neuropsychological performance on neurocognitive
419 measures described in Hypothesis 2.

420 **4b:** Changes in sleep parameters identified in Hypothesis 1 will correlate with changes in
421 neurochemistry as outlined in Hypothesis 3d and 3e above.

423 **2) Lay Summary (approximately 400 words)**

424 Sleep disturbance is nearly ubiquitous among individuals suffering from PTSD and is a major problem
425 among service members returning from combat deployments. Recent evidence suggests that adequate
426 restorative sleep may a crucial component in the ability to generalize fear extinction learning, and
427 ultimately may be a key feature in the process of recovery from PTSD. The proposed study aims to test a
428 novel, inexpensive, and easy to use non-pharmacologic approach to improving sleep among service

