Actigraphic Sleep Measurement: Daily sleep, activity, and light exposure will be collected via the Respiromics Actiwatch Spectrum®. This actigraphic wrist-watch device uses a built-in accelerometer to unobtrusively measure and record ambulatory activity levels and sleep 24 hours a day. This data can then be analyzed via sleep analysis software (Actiware 5®) that includes algorithms that transform activity data into probable sleep periods. The Actiwatch Spectrum also includes three-color light sensors that provide irradiance and luminous lux recordings in three-color bands of the visible spectrum, including red, green, and blue (Figure 17). The light sensor will be used to verify that subjects are in fact undergoing the daily light treatment and will permit covariation of other daily light sources in the statistical analyses. The device also records periods of off-wrist time to determine compliance. Data

[figure not shown]

Figure 16. Participants will maintain the device at arms length within the peripheral vision for 30 minutes each morning.

[figure not shown]

Figure 17. Actiwatch Spectrum and Actigram: The device collects wrist activity data (black bars) that are translated into sleep/wake periods (white/red bars at bottom of graph), as well as minute by minute light exposure (yellow = total light; blue = blue light; green = green light; red = red light).

FORM: Application for Human Research

| NUMBER | FORM DATE | PAGE |
|--------|-----------|----------|
| F200 | 02/2014 | 30 of 44 |

997 will be scored by the Actiware 5® program, checked for validity, and summary indices of total sleep time,
 998 sleep efficiency, sleep onset latency, wake after sleep onset (WASO), and fragmentation index will be
 999 calculated for each day and averaged across the study period.

1000 **Compliance Monitoring:** Compliance with the study requirements will be monitored in
 1001 several ways. First, participants are required to log into the internet each day to complete the sleep diary
 1002 and report timing of light usage. This is an effective means for monitoring general compliance. On-line
 1003 compliance will be monitored, and participants will be contacted by phone and/or email if they have not
 1004 logged in for more than 48 hours. Second, use of the lights will be monitored by a recording device built
 1005 into the light device that records a time stamp each time the light is engaged. Third, participants are

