 1006 required to wear the wrist actigraph at all times. This device includes a light monitor that is sensitive to
 1007 various wavelengths of light. This light data will be evaluated at the conclusion of the study to identify
 1008 whether there is a detectable change in blue/red light during the period of reported light exposure.

1009 **Post-Treatment Assessment and Scan:** At the completion of 6-weeks of BL or PL, participants
 1010 will return to the imaging center for Visit 3 to complete an
 1011 identical series of assessment and neuroimaging tasks as in
 1012 Visit 2, as well as a repeated administration of the CAPS.
 1013 Participants will return wrist actigraphs and the goLITE
 1014 device.

1015 Please note that subjects will be offered and required
 1016 to wear earplugs and/or earphones to minimize the scanner
 1017 noise. Subjects will be able to converse with a staff member
 1018 via a microphone and speaker system at all times during the
 1019 scanning session. Subjects will be provided with an
 1020 emergency button to indicate an immediate concern.
 1021 Subjects may ask to have a scan stopped and discontinue
 1022 participation in the study at any time.

1023 **Follow-Up.** After subjects complete the study, prior
 1024 to data analysis, subjects will be sent an email (*Follow-up*
 1025 *Script.doc*) with a link to an online ICF Addendum
 1026 (*PTSD_ICF_addendum.doc*) and, if they agree, subjects
 1027 will complete a 10- to 15-minute follow-up online survey,
 1028 where they will be administered the PCL-5, PHQ-9, and be
 1029 asked about general sleep problems using the ESS and ISI.
 1030 If subjects cannot complete this follow-up online, follow-up
 1031 assessments will be administered over the phone.

D. DATA ANALYSIS

1034 **Global Statistical Analysis Approach:** Behavioral
 1035 data from the neurocognitive, sleep, and symptom measures
 1036 will be evaluated for clinical severity and transformed into change metrics from baseline to post-treatment
 1037 sessions. Baseline characteristics between subject groups will be examined using analysis of variance
 1038 (ANOVA) and chi-square tests, as appropriate, and randomization will be stratified by severity of PTSD

[figure not shown]

Figure 18. Power analyses show that the proposed sample size should be adequate to address the primary hypotheses.

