**FORM: Application for Human Research**

| NUMBER | FORM DATE | PAGE |
|--------|-----------|----------|
| F200 | 02/2014 | 31 of 44 |

1039 and gender. Randomization will consist of permuted blocks to achieve balance over time. Repeated
1040 measures analysis of variance (ANOVA) and linear mixed-model approaches will be used for the primary
1041 analyses examining the efficacy of light treatment condition on measures of mood and sleep. Between
1042 group factors will correspond to the two light conditions (BL vs PL) and will control for any baseline
1043 differences in demographic variables and severity scores as appropriate. Based on specific hypotheses,
1044 separate ANOVAs will be performed for each type of dependent variable (e.g., subjective sleep scores,
1045 CAPS-2 symptom scores, mood scores, MRS metabolites). The relationship between these change
1046 indices and sleep variables will be analyzed using correlation and linear regression models in SPSS. Tests
1047 for normality will be conducted for all variables. In the case on non-normality, appropriate data
1048 transformation or non-parametric techniques will be employed (e.g., Kruskal-Wallis or Friedman tests for
1049 ANOVA; Mann-Whitney U or Wilcoxon for 2-group comparisons). Inflation of Type I error will be
1050 controlled first through the use of planned comparisons based on the hypotheses and the use of protected
1051 omnibus F-tests. Post-hoc analyses will be undertaken with protected comparisons (e.g., Tukey) or
1052 Bonferroni adjustment. Functional MRI data will be analyzed using statistical parametric mapping
1053 (SPM8) software, implementing the general linear model to compare pre- to post-therapy changes in
1054 functional responses between the active and placebo groups and across diagnostic groups, and sleep
1055 variables will be tested as covariates in the models. Finally, proton spectroscopy data for each of the
1056 metabolites will be quantified and compared for pre- to post-therapy changes in metabolite concentrations
1057 between the active and placebo treatment groups and across diagnostic groups. Type I error during
1058 neuroimaging will be controlled via whole brain False Discovery Rate (FDR) correction or small volume
1059 corrections using Family Wise Error (FWE) rate within *a priori* specified regions of interest. To handle
1060 missing data, we will first determine the potential cause of the data loss. Statistically, missing data can be

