1061 considered as falling into three types: 1) missing completely at random, 2) missing at random, or 3)
1062 missing not at random. The type of missing data will dictate the approach. Assuming type 1, and that the
1063 number of missing values is low, we will use a standard listwise deletion procedure. However, assuming
1064 that a larger number of values is missing, and data are not missing completely at random, we will be able
1065 to apply missing data imputation methods.

1066 **Power Analysis:** A power analysis based on a proposed sample size of 90 subjects suggested that
1067 with an omnibus 2 between-groups (BL vs. PL) x 2 within-subjects (pre- vs post-treatment) mixed design,
1068 assuming a moderate effect size ($f = .25$), and $\alpha = .05$, there should provide be adequate power to detect
1069 most effects. First, the primary hypotheses of the study focus on interaction effects across groups (i.e.,
1070 treatment x session interactions), which will have exceptional power ($1-\beta = 0.99$) to detect a moderate
1071 effect size at $\alpha = .05$ (see Figure 18A). Paired comparisons within each group of will also have excellent
1072 power of .91 to detect moderate effect size changes ($d = .50$), with 2-tailed tests (see Figure 18B).
1073 Without regard to group differences, a sample size of 90 would yield power = 0.84 to detect a moderate
1074 linear association (i.e., $r \geq .30$) between a predictor variable (e.g., average sleep; change in sleep
1075 parameters, PTSD symptom severity; neurocognitive performance; etc.) and an outcome variable (e.g.,
1076 fMRI signal intensity changes; spectroscopic metabolite changes; etc.), with a two-tailed test at $\alpha = .05$
1077 (see Figure 16). Thus, the proposed sample size of $n = 45$ per group appears to provide adequate power
1078 for testing the major hypotheses of the proposed study.

FORM: Application for Human Research

| NUMBER | FORM DATE | PAGE |
|---------------|------------------|-------------|
| F200 | 02/2014 | 32 of 44 |

1079 **Functional Image Pre-Processing:** Functional neuroimaging data will be preprocessed in SPM8
1080 [123]. Following standard algorithms, functional images will be slice-time corrected, co-registered to
1081 their anatomical T1-weighted images, realigned, unwarped to correct for field inhomogeneity, normalized
1082 to the standard three-dimensional space of the Montreal Neurological Institute (MNI), spatially smoothed

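### The actigraphy averaging rule gives one value per person, which conflicts with the planned baseline-to-post-treatment contrast; the trial's post-treatment nights need to be stated

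*Combined protocol and SAP*

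**What the plan says.** Section 7, Actigraphic Sleep Measurement, lists total sleep time, efficiency, onset latency, WASO and fragmentation. Each is to be "calculated for each day and averaged across the study period". No other rule for summarising actigraphy is given.

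The watch is issued at Visit 1 and worn for about a week before Visit 2. Randomisation follows at the end of Visit 2, and the watch is returned at Visit 3 after six weeks of treatment (General Procedure; At Home Six-Week Light Exposure Treatment; Post-Treatment Assessment and Scan).

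Hypothesis 1a compares the arms on "measures of sleep duration and quality as measured by actigraphy, sleep logs, sleep scales, and" polysomnography. Section D says that behavioural data, sleep included, "will be evaluated for clinical severity and transformed into change metrics from baseline to post-treatment" sessions. It puts sleep among the primary "analyses examining the efficacy of light treatment condition on measures of mood and sleep". The Power Analysis rests on "treatment x session interactions), which will have exceptional power". Hypothesis 4a begins "Changes in sleep parameters identified in Hypothesis 1 will correlate with" and goes on to cognitive improvement.

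For the pilot, the Preliminary Data section reports: "We compared actigraphic sleep between the baseline week and the final week of the study". General Procedure says that the trial's procedures will be essentially the same as the pilot's.

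**The concern.** A change score and a treatment-by-session interaction need two values per person. The averaging rule yields one. On the literal reading, that value covers about 7 untreated and 42 treated nights. If the study period means only the six weeks named in the heading above the paragraph, there is still only one value and no baseline.

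For questionnaires and laboratory tests, Section D's sessions are simply Visits 2 and 3. Actigraphy is a continuous record, so somebody has to choose the nights. The baseline nights can be inferred, since only Visit 1 to Visit 2 is untreated. The post-treatment nights are not stated for this trial. A final-week mean and a six-week mean estimate different effects unless the effect is constant from the first week, and an unstated choice between them could be made after seeing results by arm. The outcome is one of those that bear on Hypothesis 1a.

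**Working it through.** **1. The plan's own power figure.** Inputs from the Power Analysis: N = 90, f = 0.25, alpha = 0.05, two sessions, stated power 0.99. The correlation between sessions is not given, so it is an assumption. With lambda = f² × N × 2 / (1 − rho) and 1 and 88 df:

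- rho = 0.5: lambda = 0.0625 × 90 × 2 / 0.5 = 22.5, power 0.997
- rho = 0, 0.25, 0.75: power 0.913, 0.969, above 0.999

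The stated figure reproduces at rho = 0.5. It presupposes separate pre and post values. With a single average there is no session factor, and the interaction cannot be estimated.

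**2. How much the choice of nights changes the group difference.** Assume three weekly effect profiles for treatment weeks 1 to 6, as fractions of the final-week effect, with 0 in the baseline week:

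| Profile | Sum | All seven weeks (sum/7) | Six treatment weeks (sum/6) |
|---|---|---|---|
| Constant (all 1) | 6.0 | 86% | 100% |
| Half to full (0.5, 0.6, … 1.0) | 4.5 | 64% | 75% |
| Linear (k/6) | 3.5 | 50% | 58% |

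The last column measures the real ambiguity. The seven-week column applies only if the literal average were used for Hypothesis 1a. For scale, the pilot's difference in gain was 15.0 − 8.1 = 6.9 minutes (11 concussion patients). Seven-week averaging would show 5.9, 4.4 or 3.5 minutes of that.

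**3. Power for the usable options.** Assumptions: 45 per arm, two-sided alpha 0.05, equal weekly SDs (set to 1), the same correlation r between any two weeks, final-week effect 0.5 SD. Power is from the noncentral t with noncentrality = effect / (SD × √(2/45)); 88 df for the change score, 87 with the covariate. Variances:

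- Final-week change score: 2 − 2r = 1.40, 1.00, 0.60 at r = 0.3, 0.5, 0.7
- Final week, baseline as covariate: 1 − r² = 0.91, 0.75, 0.51
- Six-week mean, baseline as covariate: (1 + 5r)/6 − r² = 0.327, 0.333, 0.260

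| Analysis | r = 0.3 | r = 0.5 | r = 0.7 |
|---|---|---|---|
| Final-week change score | 0.51 | 0.65 | 0.86 |
| Final week, adjusted | 0.69 | 0.77 | 0.91 |
| Six-week mean, adjusted, constant effect | 0.98 | 0.98 | >0.99 |
| Six-week mean, adjusted, half to full | 0.87 | 0.86 | 0.93 |
| Six-week mean, adjusted, linear | 0.67 | 0.66 | 0.77 |

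The final-week rows do not depend on the profile. The adjusted six-week mean has more power in six of the nine cases and the adjusted final week in three (linear). In this design f = (difference in change)/(4 SD), so the plan's f = 0.25 is a 1.0 SD difference. At that size both adjusted analyses have power of at least 0.997 in every case, and the window hardly affects power.

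**The case against.** The strongest reply is that nobody would use the literal average for Hypothesis 1a. Section D plans a pre/post contrast, the actigraphy paragraph describes device scoring and not the efficacy outcome, and the Power Analysis gives a whole-period mean a separate use, listing a correlation "between a predictor variable (e.g., average sleep; change in sleep" parameters and an outcome. That stands. A reader might infer that the trial will test its hypothesis on a diluted average; the documents do not support that. They show a summary rule that does not fit the planned analysis and is not limited to the correlational use.

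Second, the documents do point to a window: the pilot used baseline week against final week, and the trial's procedures are to follow the pilot. It would be too strong to say that they are silent. But the link is indirect, and the trial's own sentence on averaging says something different.

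Third, daily values are calculated, and Section D allows linear mixed models, which can take repeated nightly or weekly values. So no data are lost. A mixed model would still need a stated contrast: which weeks against baseline.

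Fourth, a reader might take the dilution to mean that pooling always costs power. It does not. At 0.5 SD and r = 0.3, the unadjusted seven-week mean has power 0.89 (constant) or 0.66 (half to full), against 0.51 for the final-week change score. Setting that mean against adjusted analyses would mix dilution with the gain from the covariate, so the case does not rest on it.

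Finally, reach is limited. The visit-based sleep scales and the MSLT are unaffected.

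**Conclusion.** The inconsistency is real and should be fixed. Followed as written, the averaging rule gives one value per person and cannot feed the change metric, the treatment-by-session contrast or Hypothesis 4a, and the trial's post-treatment nights are only hinted at through the pilot.

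The size is moderate. Under the assumed profiles, a six-week mean shows 100%, 75% or 58% of the final-week difference, so the unstated choice can change the reported effect materially. It would be wrong to infer that the stated power of 0.99 or the sample of 90 is in error; neither is affected. The percentages rest on assumed profiles and the power figures also on assumed weekly correlations, because the documents give neither.

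**What to change.** In Actigraphic Sleep Measurement, replace the averaging phrase with: averaged separately over the baseline week (Visit 1 to Visit 2) and over the final 7 days before Visit 3. This matches the pilot.

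In Section D, add that BL and PL are compared on the final-week mean with the baseline-week mean as covariate, and that the same two windows give the Hypothesis 4 change scores. A six-week treatment mean can be a stated sensitivity analysis. Keep any whole-period average only for the average-sleep correlations in the Power Analysis.

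The cost is two or three sentences and no new data. The covariate is a separable improvement on Section D's change score; if change scores are kept, the windows must still be named. The real downside is precision: a final week has fewer nights, and if the effect is constant its adjusted power at 0.5 SD is 0.69/0.77/0.91, against 0.98/0.98/>0.99 for the six-week mean. In return, the estimate is not diluted if the effect builds up over the treatment period.
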